#### Safety Analysis Set (SAF)

This patient set includes all patients who were randomized and received at least one dose of study drug. It will be the main analysis set for presentation of safety. Patients will be analyzed according to the actual treatment.

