B.01	Informed consent not available/not done LABEL: Informed consent not available	Based on direct assessment, not simply the tick box (which is A1.09). Date of informed consent missing or no signature on patient's "Declaration of Informed Consent" In this case: Patient's data will be removed from database and not be used at all.	All analyses #
B.02	Informed consent too late LABEL: Informed consent too late	Informed consent date was after Visit 1, i.e., after any screening procedure	None

Table 6.2: 1 (cont'd) Handling of iPDs

Category / Code	Description	Comments	Excluded from ¹
C	Trial medication and randomisation		
C1	Incorrect trial medication		
C1.01	Incorrect medication received by patients in Placebo arm	
Placebo patient who received ≥ 1 vial (150mg) of BI 655130 verum overall /at any dosing visit
 
Can only be finally judged after DBL since unblinding information is required
	PPS
C1.02	Incorrect medication received by patients in BI arms	
BI patient who received BI dose not matching treatment that was randomized would be considered an iPD.
 
BI 655130 treated patient who fulfils any of the following:
 
For 300mg SD patients,
 
 received ≥ 1 vial (150mg) of BI 655130 verum different from planned at any visit 
For 450mg q4w patients,
 
 received any 2 vials (300mg) of BI 655130 verum different from planned at any visit or overall 
For 1200mg q4w patients,
 
 received any 3 vials (450mg) of BI 655130 verum different from planned at any visit or overall 
Can only be finally judged after DBL since unblinding information is required
	PPS

Table 6.2: 1 (cont'd) Handling of iPDs

Category / Code	Description	Comments	Excluded from ¹
C2	Non-compliance		
C2.01	Non-compliance with study drug intake – administered dose too low	Administered overall infusion volume is less than 80% of the total planned volume (except that infusion is interrupted due to safety concerns, as described in CTP section 4.1.4). The total planned volume is 
 • 100mL if discontinuation before visit V2 • 100 mL at each visit (200mL total) if discontinuation before V4 • 100 mL at each visit (300mL total) if discontinuation before V5 The total planned volume overall is 300 mL.	PPS
C2.02	Wrong treatment schedule	Patient received treatment 2 weeks outside scheduled time.	PPS
C3	Randomisation not followed		

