The discussion of all exceptional cases and problems and the decisions on the allocation of patients to populations will be made at latest at the DBLM. A separate DBLM will be performed prior to each database snapshot of this trial.

Handling of Treatment Misallocations in Analysis Sets

If a subject is randomized but not treated, they will be reported under their randomized treatment group for efficacy analysis according to RS, m-RS, and PPS (per the intent-to-treatment principle). By definition, however, such patients are excluded from the safety analyses as no study medication was taken.

If a subject is treated but not randomized, they will be excluded from both efficacy analysis and safety analysis by definition. However, subjects under such circumstances will be summarized in the final clinical trial report.

If a subject is randomized but took incorrect treatment during the study, then:

- For efficacy analyses according to RS, m-RS, and PPS, they will be reported under their randomized treatment groups. But if the subject has an iPD as defined in [Section 6.2](#), the subject will be excluded from PPS for efficacy analysis.
- For safety analyses using the SAF,
 - if a subject is planned with multiple dose administrations of BI 655130 (randomized to 450mg q4w, 1200mg q4w), they will be reported under their randomized treatment group for safety analysis because the overall safety profile will be driven by the amount of drug received in totality over the entire treatment duration. It is not likely that the safety profile will deviate from the planned treatment regimen if the subject receives only one or two vials of the incorrect medication at only some dosing occasions.
 - if a subject is planned with a single dose administration of BI 655130 (randomized to 300mg SD), they will be reported under BI 655130 300mg SD if the subject receives at least one dose of BI 655130 at any visit. A subject will be assigned to the placebo treatment group only if they don't receive any BI 655130 during the entire treatment period.
 - if a subject is planned with placebo treatment, they will be reported under placebo if no treatment with BI 655130 is received at any visit. If the subject receives $> = 1$ vial ($> = 150$ mg) of BI 655130 during the entire treatment duration, they will be reported as BI 655130 300mg SD treatment group.

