7.8.1 Adverse events

AEs will be coded with the most recent version of MedDRA. Patients will be analysed according to the actual treatment received.

The exposure adjusted incidence rate (per 100 subject years) of a selected treatment emergent adverse event is defined as the number of subjects experiencing the adverse event per treatment group during time at risk divided by the total time of subjects at risk in that treatment group to contribute the event to the analysis multiplied by 100 (per 100 subject years), where:

$$\text{Time at risk [subject years]} = (\text{date of onset of TEAE} - \text{study drug start date} + 1) / 365.25$$

If, for a subject, the selected treatment emergent adverse event (TEAE) didn't occur then the time at risk will be censored at the minimum of either (date of death, [for patients who were not dosed in the extension trial] last contact date per EoS page, [for patients who were dosed in the extension trial] date of first dose in extension trial – 1 day, randomized drug stop date + 112 days, minimum of (analysis cut-off date, day 99) [if applicable, i.e. for primary efficacy and safety analysis at week 12]). For each selected treatment emergent AE, the exposure adjusted incidence rate will be calculated as:

$$\text{Incidence rate [1/100 Subject years (pt-yrs)]} = 100 * \text{number of subjects with AE} / \text{Total AE-specific time at risk [subject years]}.$$

The analyses of AEs will be descriptive in nature. All analyses of AEs will be based on the exposure adjusted incidence rates (per 100 subject years) as well as the number of patients with AEs, and not on the number of AEs. System organ classes (if applicable) will be sorted according to the standard sort order specified by the EMA. Preferred terms (if applicable) will be sorted by total frequency (within system organ class) across all treatment arms, or, if a total column across all arms is not foreseen in the table, by total frequency (within system organ class) within the BI arm.

For details on summarization of AE data, please refer to "Handling and summarization of adverse event data for clinical trial reports and integrated summaries" (16) and "Handling of missing and incomplete AE dates" (7).

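### The safety rule in SAP 6.3 keeps misallocated 450 and 1200 mg q4w patients in their randomised arm without limit, so a complete misallocation would contradict analysis by actual treatment

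*SAP*

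**What the plan says.** The general rule is as treated. Protocol 7.3 defines the safety set with "Patients will be analyzed according to the actual treatment", SAP 6.3 repeats the definition, and SAP 7.8.1 says of adverse events "Patients will be analysed according to the actual treatment received".

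The part of SAP 6.3 on treatment misallocations then covers any randomised patient who took incorrect treatment. For 450 and 1200 mg q4w patients, "they will be reported under their randomized treatment group for safety analysis because the overall safety profile will be driven by the amount" (meaning the cumulative dose). The supporting sentence considers a patient who "receives only one or two vials of the incorrect medication at only some dosing occasions".

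The other arms have a switch that depends on drug received. For 300 mg SD, "A subject will be assigned to the placebo treatment group only if they" received none of the drug. A placebo patient given at least one active vial is reported under 300 mg SD.

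SAP Table 6.2: 1, code C1.02, sets a size of error for each arm. For 450 mg q4w it is "received any 2 vials (300mg) of BI 655130 verum different from planned at any visit or overall"; for 1200 mg q4w it is three vials (450 mg). The listed consequence is exclusion from the per-protocol set only.

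**The concern.** Keeping a q4w patient as randomised is sensible for a small kit error, but the rule does not stop at small errors. Taken literally, a 1200 mg q4w patient given placebo at every visit stays in the 1200 mg safety column. Any adverse events would then be attributed to a dose never received. Because SAP 6.1 asks for the pooled BI group in safety tables, that patient would also count as exposed there. A 450 mg q4w patient given 1200 mg throughout would have events shown under the lower dose. At stake is the dose attribution of individual adverse events in small arms.

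Randomised patients who took no study medication are outside this point, since the safety set excludes them.

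**Working it through.** The documents give no figure to reproduce. The check compares the rule with its own reasoning, then works through the possible complete swaps.

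**Rule against rationale.** Inputs are the 150 mg vial used in SAP Table 6.2: 1 and three infusions (Weeks 0, 4 and 8).
- 450 mg q4w: 450/150 = 3 vials per visit, 9 in total, 1350 mg.
- 1200 mg q4w: 1200/150 = 8 vials per visit, 24 in total, 3600 mg.
- Largest error the rationale covers, reading some visits as at most two of three: 2 × 2 = 4 vials, 600 mg. That is 4/9 = 44.4% of the 450 mg course and 4/24 = 16.7% of the 1200 mg course.
- Complete misallocation: 9/9 or 24/24 vials, 100%.

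If total drug received drives safety, as the SAP argues, a completely misallocated patient belongs with the treatment received.

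**The six complete swaps from a q4w arm, three infusions.**

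| Randomised | Received (mg) | Largest error at a visit (mg) | C1.02 size (mg) | Column now | Column under the fix |
|---|---|---|---|---|---|
| 450 | 0/0/0 | 450 | 300 | 450 | placebo |
| 450 | 300/0/0 | 450 | 300 | 450 | 300 SD |
| 450 | 1200/1200/1200 | 750 | 300 | 450 | 1200 |
| 1200 | 0/0/0 | 1200 | 450 | 1200 | placebo |
| 1200 | 300/0/0 | 1200 | 450 | 1200 | 300 SD |
| 1200 | 450/450/450 | 750 | 450 | 1200 | 450 |

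The current rule gives the arm received in 0 of 6; the fix does so in 6 of 6. Planned first-infusion amounts (0, 300, 450, 1200 mg) all differ, so no patient can match two arms.

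For patients who stop after one or two infusions, one case differs. A 450 mg patient given a single 300 mg infusion has an error of 450 − 300 = 150 mg, below 300 mg, and stays in 450 mg.

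**Size per misplaced patient.**
- Dose column, planned 40: 1/40 = 2.5 percentage points.
- Pooled active column, planned 3 × 40 = 120: 1/120 = 0.8 points.
- Arm sizes after early termination are not given. Assuming 20 to 30 per arm: 1/20 = 5.0 to 1/30 = 3.3 points.
- Exposure-adjusted rate (SAP 7.8.1), assuming all 40 are at risk for 85 to 99 days: 40 × 85/365.25 = 9.31 and 40 × 99/365.25 = 10.84 subject-years. One more patient with an event adds 100/9.31 = 10.7 or 100/10.84 = 9.2 per 100 subject-years.

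**The case against.** The strongest reply is that the clause should be read with its reasons. It is then a rule for partial kit errors, and a patient given only placebo falls back to the general as-treated definition. This is a fair account of the likely intent. But the vial sentence is a justification and not a condition, the trigger is any incorrect treatment, and no other column is named for larger errors.

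Second, SAP 6.3 sends exceptional cases to the database lock meeting: "decisions on the allocation of patients to populations will be made at latest at the DBLM". For C1.01 and C1.02, Table 6.2: 1 adds "Can only be finally judged after DBL since unblinding information is required". A reader might infer that the meeting could never act in time. The documents do not support that. A separate meeting precedes each snapshot, and the sponsor analyses the first one, so codes for those patients may be open before the second. The access plan is not in the documents. What remains is that the meeting has no written rule to apply.

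Third, SAP 7 lists important deviations per patient, and SAP 7.7 summarises the mg received. At the second snapshot, which holds the primary safety analysis, these would reveal the error. They would not move the adverse events.

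Fourth, wrong kits at every infusion are unlikely, given supply through the interactive response system (Protocol 4.1.6) and the two-person check (Protocol 4.1.4). This stands, and it limits the severity.

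**Conclusion.** The point holds as a minor one. For a completely misallocated q4w patient, a stated rule gives a result contrary to the as-treated principle and to its own rationale. It is conditional: the documents report no such error and no expected frequency. At the planned arm size each case is worth 2.5 percentage points in a dose column. Safety is descriptive with no hypothesis tests (SAP 7.8), and seamless conduct of Part 2 is no longer considered viable (SAP 3).

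Two stronger readings are tempting. One is that the SAP has given up as-treated safety analysis. It has not: the principle appears in both SAP 6.3 and 7.8.1, and as-randomised reporting of small errors is defensible. The other is that the placebo and 300 mg SD rules need the same rewriting. They lack an upper limit, but each has a written switch on drug received, so the omission described here is specific to the q4w arms. Matching every arm by infusion could also move a 300 mg SD patient given 450 mg once, a 150 mg difference, into an arm with a planned total of 1350 mg.

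SAP section 4 shows no text in the available copy and the ADS Plan is not included, so neither could be checked for a limit.

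**What to change.** Amend the misallocation paragraph in SAP 6.3 for treated patients randomised to 450 or 1200 mg q4w only, applied in this order:

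- (a) Keep as-randomised reporting when the error is below the existing C1.02 size: under 300 mg for 450 mg q4w and under 450 mg for 1200 mg q4w. State it in mg, because Protocol Table 4.1.1: 3 also lists a 300 mg vial, and say whether errors at different visits are netted or summed.
- (b) Report a treated q4w patient who received no BI 655130 under placebo, as already done for 300 mg SD.
- (c) At or above the C1.02 size, report the patient under another arm when the amount at every infusion received matches that arm's plan. Otherwise keep the patient as randomised and flag them beside the safety tables.

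Leave the placebo and 300 mg SD rules unchanged.

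The cost is one paragraph and one derivation from vial data already needed for C1.01 and C1.02. A rare patient changes safety column, and assignment can be final only after unblinding. For an early stopper, (c) may rest on one infusion. Matching is exact, so a 450 mg patient given 1200/1200/1050 mg, or a 1200 mg patient given 750 mg, is flagged and not moved.

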6.5 POOLING OF CENTRES

For the main analyses of efficacy to be performed in this trial, all patients from all centres will be pooled for statistical analysis. The effect of region on the primary and selected secondary efficacy endpoints will also be investigated as described in [Section 6.4](#).

6.6 HANDLING OF MISSING DATA AND OUTLIERS

Section 7.5 of the CTP describes the handling of missing data.

The original results (OR) approach implies the presentation of data exactly as observed (not using time windows and not setting values to missing).

OR analysis will be performed on parameters and endpoints that are either not affected by patients' rescue medication use (e.g. plasma concentration level of BI 655130, rescue medication use itself), or, if it is not meaningful to apply any imputation rule for the replacement of missing values.

6.6.1 Withdrawals

The reasons for withdrawal from treatment will be reported as indicated on the eCRF.

6.6.2 Efficacy endpoints

Based on the different reasons for patients' data missing for different endpoints, various approaches will be used to assess the impact of missing data on the efficacy endpoints of this trial, depending upon the type of the endpoint. Approaches to be applied are described below.

Missing data imputations will be performed using all available on-treatment data observed up to the respective analysis cut-off date.

Binary efficacy endpoints

With regards to the handling of missing data on binary efficacy endpoints, the following table gives an overview of the proposed imputation methods which are described in more detail below.

Table 6.6.2: 1 Missing data approaches for binary efficacy endpoints

	Binary efficacy outcome observed or not	Imputation Approach Subsequent to Event of Type		Missing due to Other reasons - Withdrew consent - Loss of follow up - Data not collected - etc.
		Rescue intake	Death due to any cause	
NRI	Observed	NRI	n.a.	n.a.
	Not observed	NRI	NRI	NRI
MI	Observed	MI	n.a.	n.a.
	Not observed	MI	MI	MI
MI-NRI	Observed	NRI	n.a.	n.a.
	Not observed	NRI	NRI	MI
OC	Observed	no imputation	n.a.	n.a.
	Not observed	no imputation	no imputation	no imputation

Primary Imputation Approach – No Response Imputation [NRI]

1. If a patient takes a rescue medication (as defined in [Section 5.4.5](#)) for the treatment of ulcerative colitis or died due to any cause prior to observing the primary endpoint for this trial, then all data subsequent to the intake of such rescue will be considered to be missing.
2. For endpoints which are measured at multiple visits (thereby excluding the endpoints which are based upon the endoscopic subscore), if there are data at visits both before and after the visit with a missing outcome, then impute as success only if both neighbouring visits also represent a success (independent of whether the preceding and following observations were selected for analysis based on time windows described in [Section 6.7](#)) with no intervening use of rescue medication;

For all patients with a missing visit outcome, impute as a failure to achieve a response.

Other Imputation Approaches

- Observed cases (OC) approach: first, set all data collected after intake of a rescue medication to missing; then include all collected data with no imputation performed on the missing data. The analysis using OC approach is only based on all patients who have non-missing values in the patient set.
- Multiple Imputation (MI) approach: use baseline and on-treatment data only, and impute each Mayo Clinical Score component (SFS, RBS, PGA and mESS) as ordinal variables with values 0, 1, 2 and 3. The imputation will be done using OC data as the input dataset, and will follow the steps outlined below:
 1. *Multiple Imputation of Missing data:* use SAS procedure PROC MI with the Fully Conditional Specification (FCS) method and corresponding options/statements. Logistic regression method is used to impute missing values by using the ordering of the class level in each variable.

The subscore variables (SFS_v, RBS_v, PGA_v, mESS_v) represent the corresponding subscore at each visit, where v=2 (baseline), 3 (Visit 3), 4 (Visit 4), 5 (Visit 5) and 6 (Visit 6). All variables are treated as ordinal variable from 0 (best) to 3 (worst). For each imputed subscore at specific visit, the subscore at other visits and all other subscores at each visit are used as covariates together with the treatment and stratification factors (previous BIO experience and prior corticosteroid use).

```
PROC MI DATA=alldat seed=1000 out=outmcs;  
  CLASS SFS2-SFS6 RBS2-RBS6 PGA2-PGA6 mESS2 mESS6 trt stratum;  
  FCS nbiter=10 logistic(SFS2-SFS6 RBS2-RBS6 PGA2-PGA6 mESS2 mESS6  
/details);  
  VAR SFS2-SFS6 RBS2-RBS6 PGA2-PGA6 mESS2 mESS6 trt stratum;  
RUN;
```

Note that the seed 1000 will be used throughout. If a second seed is required, 1001 will be used, and so on as necessary.

2. *Analysis of Completed Datasets*: For each completed dataset after multiple imputation, it will be used to calculate the clinical mayo score related endpoints, e.g., clinical remission, clinical response, endoscopic improvement, etc, and to perform the corresponding statistical analysis as specified in [Section 7](#).
3. *Combine Results*: PROC MIANALYZE combines the analysis results from step 2 and generates valid statistical inferences by accounting for the variability introduced by the MI process.

If the above imputation model cannot impute without error on the trial data, then it will be abandoned and an alternative model will be used whereby only subscores (SFS, RBS, PGA, mESS) at visit 6 (primary analysis time point) will be treated as ordinal variables and at all other visits subscores will be treated as continuous variables. If this alternative model also cannot impute without error, then it too will be abandoned and a further, even simpler, model will be implemented which will impute the primary binary endpoints, clinical remission of Yes or No at visit 6, directly (rather than at the subscore level); this model will include prior subscores at visits 2, 3, 4 and 5 as continuous variables.

- Combined MI and NRI approach (MI-NRI): If a patient takes a rescue medication for the treatment of ulcerative colitis or died due to any cause prior to observing the primary endpoint for this trial, impute as a failure to achieve response. For all OTHER patients with a missing visit outcome, a missing at random assumption will be made, and imputation will be done using the MI approach as described above.

Continuous efficacy endpoints

- Primary approach (MMRM): for efficacy endpoints which are continuous in nature, the use of a restricted maximum likelihood (REML)-based mixed model repeated measures (MMRM) approach, if applicable, will ensure that missing data are handled implicitly, via a missing at random assumption, by the statistical model. The model will include on-treatment data only and OC data as the input dataset.
- Multiple Imputation (MI) approach: use on-treatment data only and OC data as the input dataset, will impute each continuous endpoint follow the steps outlined below:
 1. *Multiple Imputation of Missing data*: use SAS procedure PROC MI with the Fully Conditional Specification (FCS) method and corresponding options/statements.

The continuous variables, i.e., IBDQ_v represent the IBDQ overall score at each visit, where v=2 (baseline), 3 (Visit 3), 4 (Visit 4), 5 (Visit 5) and 6 (Visit 6). Regression method is used to impute missing values. For each to-be imputed IBDQ overall score at a specific visit, the non-missing overall scores are used as covariates together with the treatment and stratification factor (previous BIO experience and prior corticosteroid use).

```
PROC MI DATA=alldat seed=1000 out=outmcs;  
  CLASS trt stratum;  
  FCS nbiter=10 reg(/details);  
  VAR IBDQ2-IBDQ6 trt stratum;  
RUN;
```

Note that the seed 1000 will be used throughout. If a second seed is required, 1001 will be used, and so on as necessary.

2. *Analysis of Completed Datasets*: For each completed dataset after multiple imputation, it will be used to perform the corresponding statistical analysis as specified in [Section 7](#).
 3. *Combine Results*: PROC MIANALYZE combines the analysis results from step 2 and generates valid statistical inferences by accounting for the variability introduced by the MI process.
- Observed Case (OC) approach is the same as described above for the binary efficacy endpoints

